3.5. Exploratory Endpoint(s)

Allergist Adherence to the PPA Guidelines (Figure 5). Allergist adherence will be assessed once progress notes by the allergist to whom the infant was referred to have been added to the patient EHR and will be determined based on the following four data elements:

1) Skin Prick Test result (0-2 mm, 3-7mm, ≥ 8 mm), 2) peanut sIgE results, 3) results of in-office supervised feeding of peanut products or oral food challenge with peanut products and 4) peanut product introduction/feeding recommendation. These data will be extracted from laboratory test results, if available, and the allergist progress note entered into the patient EHR. If any data elements are missing, however, the allergist adherence will be adjudicated by an expert panel of allergists from the study advisory board.

Figure 5. Allergist Adherence

*We assume that allergists will evaluate any child who is referred to them.

[figure not shown]
Barriers/facilitators for PPA Guideline adherence among pediatric clinicians and caregivers. Barriers and facilitators will be assessed through survey of pediatric clinicians and caregivers.

Caregiver adherence (peanut product introduction and feeding frequency) (Figure 6). Caregiver adherence is conceptualized to be independent of the clinician's adherence. All pathways to adherence (whether full adherence, meaning the clinician and the caregiver adhere, or caregiver adherence despite conflict with clinician recommendation) are described in Figure 6. Caregiver adherence to the PPA Guidelines will be assessed through the caregiver survey completed around the child's first and second birthdays, as well as through the child's EHR records.

[figure not shown]
Caregiver adherence will be determined based on the following five data elements: 1) infant risk category (high- vs. low-risk based on the presence of an egg allergy and/or severe eczema), 2) peanut sIgE testing results, if applicable (negative vs. positive); 3) peanut skin prick test results (if applicable), 4) peanut product introduction (introduced or did not introduce), and 5) peanut product feeding frequency and quantity (feedings per week). These data will be obtained from the caregiver survey (which will assess the timing, amount, frequency, and modes of peanut product consumption by the infant) and from the infant's EHR records (risk category, testing recommended, and testing results).

For low-risk infants, the caregiver is adherent if the caregiver introduces peanut by 12 months of age. For high-risk infants, the caregiver is adherent if the clinician's testing indicates the introduction of peanut and the caregiver introduced peanut products by 7 months of age and continued feeding at least 6g over ≥ 3 feedings per week as reported around the infant's 1st birthday or the clinician's testing indicates avoidance of peanut and the caregiver does not introduce peanut products as reported around the infant's 1st birthday. For high-risk infants, the caregiver is partially adherent if the pediatric clinician and/or allergist's testing supports the introduction of peanut, and the caregiver introduces peanut products but does not do so by 6 months of age or does not continue feedings with at least 6 gm of peanut protein or over ≥ 3 feedings per week as reported around the infant's 1st birthday.

Figure 6. Caregiver Adherence

High Risk

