- d. *A BPA* triggered when the pediatric clinician views peanut sIgE results (for those patients for whom sIgE has been ordered. The BPA will provide the criteria for "positive" results (≥ 0.35 kU/L) and a recommendation to refer to an allergy specialist if results are positive.

Caregiver Handout on How to Introduce Peanut Containing Products: Handout adapted from the NIAID caregiver materials (English and Spanish versions). The handouts were simplified and tested with caregiver groups including low-literacy, underserved families. This handout can be used as part of pediatric clinician counseling and can go home with caregivers as a reminder.

C. Follow-up Prompts at 9- and 12-month WCC: *Smart Texts and Data Elements* that advise the pediatric clinician to ask caregivers and chart whether peanut products have been introduced into their infant's diet. If the caregiver reports that peanut products were introduced, the clinician will be directed to document whether introduction was tolerated. If caregiver reports that peanut products were not introduced, the clinician will be directed to ask the caregiver for reasons why they did not.

Note: For those practices that do not use an Epic-based EHR, Lurie Children's study team will facilitate and work with their informatics teams to implement an iteration of the CDS tool that is compatible with the practice EHR.

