13.4.5 Analyses of Exploratory Endpoint(s)

All analyses will be provided separately for high- and low-risk groups as noted. The entire infant sample of both risk groups will also be analyzed together where noted. Analyses will be treated as exploratory and hypothesis- generating, so no formal correction for multiple testing will be applied.

Allergist adherence will be analyzed with generalized linear mixed models for high-risk infants in the EEDI1 sample in the same manner as the primary pediatric clinician endpoint with infants as the unit of analysis. The allergist adherence endpoint will be determined as follows:

An allergist is adherent if:

- The allergist recommends introduction following a sIgE test ≤ 0.35 , a skin prick test 0-2mm, a successful supervised feeding or a successful oral graded food challenge.
- The allergist recommends avoidance and continued monitoring after a skin prick test ≥ 8 mm or a failed supervised feeding or oral graded food challenge.

An allergist is non-adherent if:

- The allergist fails to recommend introduction following a sIgE test ≤ 0.35 , a skin prick test 0-2mm, a successful supervised feeding or a successful oral graded food challenge.
- The allergist recommends introduction following a skin prick test 3-7mm without performing a supervised feeding or oral graded food challenge.
- The allergist recommends introduction following a skin prick test of ≥ 8 mm.

Caregiver adherence (yes/no) will be analyzed with generalized linear mixed models in the EEDI2 sample in the same manner as the primary pediatric clinician endpoint with infants as the unit of analysis. Only high risk infants with data on clinician and/or allergist testing will be used in the analysis of caregiver adherence. For the high risk infants in the primary analysis of the exploratory endpoint, partial caregiver adherence (as defined below) will be grouped with non-adherence. The caregiver adherence endpoint will be determined as follows:

For low-risk infants:

- A caregiver is adherent if the caregiver introduces peanut by 12 months of age, regardless of the pediatric clinician's recommendation.
- A caregiver is non-adherent if the caregiver does not introduce peanut by 12 months of age, regardless of the pediatric clinician's recommendation.

For high-risk infants:

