- A caregiver is adherent if the pediatric clinician and/or allergist's testing supports the introduction of peanut, and the caregiver introduces peanut products by 7 months of age and continues feedings with at least 6 g of peanut protein over ≥ 3 feedings per week as reported around the infant's 1st birthday ..
- A caregiver is adherent if the pediatric clinician and allergist's testing supports the avoidance of peanut and the caregiver does not introduce peanut products as reported around the infant's 1st birthday.
- A caregiver is *partially adherent* if the pediatric clinician and/or allergist's testing supports the introduction of peanut, and the caregiver introduces peanut products but does not do so by 6 months of age or does not continue feedings with at least 6 gm of peanut protein or over ≥ 3 feedings per week as reported around the infant's 1st birthday.
- A caregiver is non-adherent if the pediatric clinician and/or allergist's testing supports the avoidance of peanut, and the caregiver introduces peanut products as reported around the infant's 1st birthday.

The primary analysis of the exploratory endpoint will be repeated in the EEDI2 sample including pediatric clinician adherence, allergist adherence (high-risk only) and two-way interactions with each other and intervention group, as fixed effects predictors.

The primary analysis of the exploratory endpoint will be repeated in the EEDI2 sample by combining adherence and partial adherence and comparing partial and non-adherence.

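### The written scoring rules for caregiver adherence in high-risk infants overlap and leave gaps, most clearly when clinician and allergist testing disagree

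*Combined protocol and SAP*

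**What the plan says.** Two sections of the combined protocol and SAP define caregiver adherence for high-risk infants.

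- **Section 3.5** ties both routes to adherence to the clinician's testing. The avoidance route applies when "the clinician's testing indicates avoidance of peanut and the caregiver does not introduce peanut products". Its partial-adherence rule names the pediatric clinician and/or the allergist. It has no non-adherent rule.
- **Section 13.4.5** has four rules. The introduction rule reads "A caregiver is adherent if the pediatric clinician and/or allergist's testing supports the introduction of peanut, and the caregiver introduces peanut products", with conditions on age and feeding. The avoidance rule needs both sources: "the pediatric clinician and allergist's testing supports the avoidance of peanut and the caregiver does not introduce peanut products". Partial adherence again turns on either source supporting introduction. The last rule is "A caregiver is non-adherent if the pediatric clinician and/or allergist's testing supports the avoidance of peanut, and the caregiver introduces peanut products".

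Section 13.4.5 keeps high-risk infants who have test data from either source, and groups partial adherence with non-adherence in the main analysis. A repeat analysis regroups partial adherence. Section 13.2 says the high-risk endpoints can be determined only where clinician testing is available, giving IgE and skin prick tests as examples. It refers to Figure 6 for the definitions.

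**The concern.** One infant can have two evaluations by design. The sIgE result alert gives "a recommendation to refer to an allergy specialist if results are positive" (Section 6.1.1), and the allergist may then have grounds for introduction, such as "a successful supervised feeding or a successful oral graded food challenge" (Section 13.4.5). If the two sources point in opposite directions, either-source triggers on opposing rules can both fire, while a both-sources trigger cannot fire at all.

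At stake are the exploratory comparison of caregiver adherence between arms, its repeats, and the exploratory models in Section 13.4.4 that use caregiver adherence as a predictor of peanut allergy. Where the rules give two answers or none, the analyst must choose the coding, possibly after arm-level data have been seen.

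**Working it through.** The plan states no figure on this point to reproduce, so the check is of the rules' logic.

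**Inputs.** The four high-risk rules of 13.4.5 and the rules of 3.5, taken as written. For 3.5, clinician is read as pediatric clinician; the other reading is taken up under the objection. Timely means introduced by 6 months with full feeding. This sidesteps a separate conflict: in both sections the adherent rule uses 7 months and the partial rule 6, so introduction between those ages can meet both. That also needs reconciling.

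**Step 1: sources disagree.** 2 discordant pairings × 3 caregiver behaviours = 6 patterns.

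| Clinician testing supports | Allergist testing supports | Caregiver | 13.4.5 | 3.5 |
|---|---|---|---|---|
| introduction | avoidance | timely, full | adherent and non-adherent | adherent |
| introduction | avoidance | late or insufficient | partial and non-adherent | partial |
| introduction | avoidance | not introduced | no rule | no rule |
| avoidance | introduction | timely, full | adherent and non-adherent | no rule |
| avoidance | introduction | late or insufficient | partial and non-adherent | partial |
| avoidance | introduction | not introduced | no rule | adherent |

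Under 13.4.5, 0 of 6 patterns get exactly one category: 2 + 2 are double-scored and 2 are unscored. The two sections also part company. For example, the last row is adherent under 3.5 and unscored under 13.4.5.

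**Step 2: main yes/no analysis.** Partial joins non-adherent, so the two late-or-insufficient patterns resolve to non-adherent. That leaves 6 − 2 = 4 unresolved: 2 contradictory and 2 unscored.

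**Step 3: repeat that merges adherent with partial.** The late-or-insufficient patterns now fall on both sides of the split, so all 6 are unresolved.

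**Step 4: gaps without disagreement.** If both sources support introduction, or only one is available and it does, and the caregiver does not introduce, no rule in 13.4.5 applies. If one source alone supports avoidance and the caregiver does not introduce, 13.4.5 read literally gives no category. Section 3.5 gives adherent when that source is the clinician.

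**Step 5: when disagreement can arise.** The readable text never defines when testing supports avoidance.

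- *Reading A: a positive sIgE supports avoidance.* The rules in 3.5 and 13.4.5 do assume that clinician testing can point that way. An sIgE-positive infant whom the allergist clears is then discordant.
- *Reading B: a positive sIgE means referral only,* as Sections 6.1.1 and 13.4.2 have it. A cleared infant given peanut on time is then simply adherent under 13.4.5. Disagreement shrinks to a negative sIgE followed by an allergist finding for avoidance, and neither section sends sIgE-negative infants to the allergist. An sIgE-positive infant with no completed allergist evaluation has testing that supports neither course and meets no rule, yet stays in the analysis.

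**The case against.** **The figures may settle it.** Section 3.5 says Figure 6 sets out the pathways to caregiver adherence, and Figure 8 is a caregiver pathway. Neither can be read here. A reader might infer that the plan has no order of precedence at all. The documents do not support that; only the readable text can be said to lack one. The diagnosis hierarchy in 3.4 and the expert panel in 3.5 serve other endpoints. Even if a figure gives an order, the written rules would still conflict with one another.

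**Clinician in 3.5 may include the allergist.** Section 13.2 illustrates clinician testing with skin prick tests, so this is possible. It softens the contrast: the sections can score an infant differently, but need not. Against it, the partial rule in the same paragraph of 3.5 names the two sources separately.

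**A positive sIgE means refer.** This is a fair reading. A reader might infer that every sIgE-positive infant later cleared by the allergist is double-scored. That holds only under reading A. The gaps in Step 4 remain under either reading. Section 3.5 assumes that allergists evaluate every referred child, so infants still awaiting evaluation may be few.

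**The size is unknown.** This stands. Under reading A, purely assumed inputs (10–40% sIgE-positive, 50–90% of those evaluated, 30–70% of those cleared) give 0.10 × 0.50 × 0.30 = 1.5% to 0.40 × 0.90 × 0.70 = 25.2% of tested infants. A reader might set this beside the 18-point detectable difference in 13.7. That would be wrong: a share of infants with an unclear score is not a bias in an arm difference, and 13.7 assumes the full high-risk sample. The order set and result alert exist only in the intervention arm, so affected infants could gather there, but nothing in the documents quantifies it.

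**Conclusion.** The written rules do not give every high-risk infant exactly one category. When the two sources disagree, 13.4.5 fails in 6 of 6 patterns, of which 4 matter in the main yes/no analysis and all 6 in the repeat that merges adherent with partial. It also lacks a category for testing that supports introduction followed by no introduction, whether or not the sources agree. Sections 3.5 and 13.4.5 name the source differently and can disagree about the same infant.

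These are counts of rule patterns, not of infants. The frequency rests on the undefined meaning of supporting avoidance and on rates that the documents do not give. The endpoint is exploratory and labelled hypothesis-generating, and the models that use it as a predictor are exploratory too. A reader might infer a threat to the trial's main conclusions, but no primary or secondary confirmatory analysis uses this score. Severity: minor.

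**What to change.** Before arm-level data are examined:

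1. Reconcile 3.5, 13.2 and 13.4.5 with one another and with Figures 6 and 8, including which source each rule means and the 6- versus 7-month wording.
2. Define, for scoring only, when testing supports introduction and when it supports avoidance, and say how a positive sIgE with no allergist result is treated.
3. Pre-specify one governing result per infant. The choice is the investigators'. If that result can come after the age limit for introduction, say how timing is scored.
4. State the category for testing that supports introduction followed by no introduction. A precedence rule alone would leave these infants unscored.
5. Report infants with no governing result as not determinable, by arm.
6. Add feeding and challenge results to the caregiver-adherence data elements in 3.5, which list only sIgE and skin prick results.

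The cost is protocol and SAP wording. Test dates and results are already extracted (Table 8.2), and feeding and challenge results are already collected for allergist adherence (3.5). Some infants may move to the not-determinable row. None of this takes a view on which result should guide care.

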3.6. Stratification, Randomization, and Blinding/Masking

Randomization will be accomplished through a password-protected, web-based, randomized system maintained by the Statistical and Data Coordinating Center. Practices will be randomized to intervention using a random number generator. Randomization will be stratified by size of the practice site, so that large volume practices are randomized to intervention separately from practices with fewer annual patients. Neither the control arm practice sites nor intervention sites will be blinded to their trial arm status.

3.6.1. Procedure for Unblinding/Unmasking

Not applicable.

4. Selection of Participants and Clinical Sites/Laboratories

4.1. Rationale for Study Population

- Primary care pediatric clinicians are the clinicians to whom the PPA Guidelines are primarily directed and who see the majority of infants during the time frame that peanut product introduction is recommended for high-risk infants (4-6 months).
- All infants, regardless of peanut allergy risk, are subject to the NIAID-sponsored PPA Guidelines. Infants seen by primary care pediatric clinicians working in study-participating clinics will have their EHR data extracted to determine whether pediatric clinicians in the intervention arm adhered to the PPA Guidelines more so than those in the non-intervention arm and to measure incidence of

peanut allergy.

- Caregivers are the final and most important conduits for PPA Guidelines implementation. Therefore, caregivers of infants seen at all participating practices at a 4- and/or 6-month WCC during the designated study period will be surveyed when their infants are 12 and 24 months in order to determine PPA Guidelines adherence regardless what their pediatric clinician's and/or allergist's recommendation was. In addition, caregivers will be surveyed for the presence of peanut allergy in their infant.
- Particularly for high-risk infants, allergists to whom the pediatric clinicians of the study refer infants for early dietary peanut product introduction are important for Guidelines implementation. Therefore, in order to assess adherence to the portion of the PPA Guidelines directed towards allergists, the study will review the specific management approach these allergists will use. It is anticipated that a given allergist will see patients referred by pediatric clinicians from both study arms.

4.2. Inclusion Criteria

For each of the following entities/individuals, all criteria need to be met for participation in the study:

- a) Practice sites:
 - a. The practice utilizes a centrally-integrated EHR.
 - b. The practice has signed a legally-binding engagement agreement with Lurie Children's Pediatric Practice Research Group.
 - c. The practice employs at least one physician who has completed a residency in general pediatrics and is practicing as a general pediatrician.
- b) Pediatric Clinicians:
 - a. Clinician is a physician, physician assistant, resident, advanced practice nurse, family practitioner, or pediatric nurse practitioner working in a pediatric practice.
 - b. Clinician is employed by a practice that is a member of one of the participating practices in the study.
 - c. Clinician provides well child care to infants ages 4 or 6 months.
- c) Infants:
 - a. Infant has been seen by a pediatric clinician in the intervention or control arm for a 4- and/or 6-month WCC. (Note: Because infants will be followed through EHR data extraction, inclusion of an infant's data in the study will not require caregiver consent.)
- d) Caregivers:
 - a. Is the caregiver of an infant seen for a 4- and/or 6-month WCC by a pediatric clinician in a practice belonging to the study's intervention or control arms.
 - b. Is at least 18 years of age or has parent or guardian permission to participate.
 - c. Is able to understand the study and provide informed consent for the 12- and 24-month (child's age) survey.

4.3. Exclusion Criteria

For each of the following entities/individuals, if any of the following criteria are met, they will be excluded from participation in the study:

a) Practice Site:

- a. The site sees <50 newborn patients/year.
- b. The site has only temporary pediatricians on staff (e.g., resident physicians).
- c. The practice pediatric clinicians do not use an EHR system.

b) Pediatric Clinicians:

- a. The clinician is a temporary employee.
- b. The clinician begins employment at participating practice less than three months prior to end of the 18-month study enrollment period.

c) Infants:

- a. The infant has a medical condition that chronically inhibits the ability to take food orally (i.e., dysphagia, muscular dystrophy, gastrostomy).
- b. The infant has past or current medical problems or findings that prohibit implementation of PPA Guidelines or may have impacted the quality or interpretation of the data obtained from the study. This will be identified from the caregiver survey and a post-hoc review of EHR data. .

d) Caregivers:

- a. Caregiver's primary language is not English or Spanish.
 - i) The study is presently limited to participants fluent in English and/or Spanish because practice sites have not indicated a significant patient population with additional language needs. If a need is identified, the study team will allocate resources to develop appropriate materials and obtain any needed staff for translation(s).

4.4. Selection of Clinical Sites/Labs

Thirty-seven practices that are members of the Pediatric Practice Research Group (PPRG), a pediatric practice-based research network at the Ann and Robert H. Lurie Children's Hospital of Chicago (Lurie Children's Hospital) may participate in the study. In order to account for possible attrition prior to the start of the study, the study has been designed (see **Section 13.7**) for at least 30 randomized practice sites providing adequate statistical power to test the primary hypothesis. The PPRG will ensure that all engagement agreements with practice networks or practices are completed for the participating sites. The practices are part of networks that utilize a centrally-integrated EHR system. Practice networks include but are not limited to:

1. Lurie Children's Hospital of Chicago's multi-site primary care practice (Town & Country) and Community Connect Health Exchange network. These practices share the outpatient version of Lurie Children's Hospital Epic EHR.
2. AllianceChicago, a network of community health centers that share Centricity EHRs.
3. OSF HealthCare in Peoria, IL is a network of practices that share an Epic EHR system.
4. Unity Point Health in Peoria, IL is a network that has a history of participating in practice based

research with OSF HealthCare. The practices share an Epic EHR system.

5. Known and Potential Risks and Benefits to Participants

5.1. Risks of Investigational Product or Intervention as cited in Investigator Brochure or Package Insert

Not Applicable

